### 1. Multiple tests and p-value hunting/hacking

We recognise that there are no perfect ways of exploring such data. There are many areas where exploration of associations, e.g. between plausible predictor and response variables can usefully be informed by null hypothesis testing. As there are many such associations, this raises the classical "multiple tests" issue: that if all the null hypotheses about the population were true (and independent) then the expectation of a single test being "significant" at the alpha level (.05) rises rapidly, and markedly above .05, as the number of tests rises. This issue has of course been know from the invention of hypothesis testing, for a readable early discussion in relation to mental health research see (e.g. Grove & Andreason, 1982). This leads to two related issues: the simple one of the elevated "studywise" false positive rate, and the issue of "p-value hunting/hacking" (touched on as part of the recent resurgence of interest in trying to reduce the dangers of naïve use of hypothesis testing, e.g. (Amrhein et al., 2019; APA, 2016; Wasserstein & Lazar, 2016).

There is an extensive literature with arguments for and against application of methods to reduce the overall "studywise" false positive rate to .05, and various methods by which to do this (Primo de Carvalho Alves & Sica da Rocha, 2019 e.g.). Given the diversity of areas in which we will be exploring associations and where null hypothesis significance testing (NHST) has some value as a decision rule, we do not propose to use any of the methods of controlling for the inevitably elevated false positive rate. However, we do propose to be consistent and clear in recognising the risk. All hypothesis tests will be reported with the actual p value, not as "p < .05" versus "NS" (or some other ordinal categorisation of p values by asterixes). Where possible, 95% confidence intervals (CIs) will be reported for all statistics. To be precise, we will report the Bias Corrected Adjusted, (bca) 95% CI from 1000 bootstrap replications unless it is not available in which case the percential CI will be used, see (Carpenter & Bithell, 2000; Puth et al., 2015).

That issue of the inflated type I error rate that is bound to arise from there being multiple questions of interest leads to the option for deliberate or uninformed "p-value

© CE & CP for ITAMITED group

Page 2 of 14

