# 3. Primary objective: Effectiveness of ITAMITED as it is applied routinely in its natural context.

We will analyse effectiveness with three complementary analyses performed for data/analysis tranches 2 and 3.

(a) Baseline/termination change. This is has been the traditional focus of many existing explorations of effectiveness of treatment. We will report both mean change and also effect sizes reporting Cohen's d2 and dz (Cohen, 1988) (the ratio of mean change to baseline SD and the ratio of mean change to SD of change respectively) and report these with bootstrap CIs. As well as reporting the global aggregate mean shifts with bootstrap 95% CI for each score. We will report the regression of termination scores on baseline scores and the distributions of change scores.

We will explore the impact of baseline variables: gender, age, diagnosis, demographic

variables, medication use and service on change. These predictor effects will be explored entering them as predictors of termination scores/values in ANOVA models with attention paid to the almost certain violation of assumptions of the ANOVA and exploration of mitigation of those violations. As gender and age are such crucial variables in Eating Disorders (Eds) the effects of entering these as predictors (or analysing separately be gender) on effects of other variables will be reported.

To address individual change we will report the Jacobson plot of termination against baseline scores for all scores and report the RCSC breakdown of change on each measure where it is possible to define the CSC and RCI.

(b) Multilevel models (MLM) of rates of change. MLM allows analysis of change slopes across diverse durations of therapy/ascertainment and the method handles the nonindependence of observations arising from the repeated measures within participant appropriately. These analyses can give a much more nuanced picture of change than baseline/termination analyses while allowing exploration of the effects of the same predictors and covariates analysed in (a). As for (a), durations of therapy are not directly reflected in the analyses though in contrast to (a), all data across all durations of data collection are used rather than just the first and last values.

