### 2. Study the psychometric properties of the self-report measures.

To explore the baseline, cross-sectional psychometric properties of the self-report measures (tranche 1). The analyses will be as follows.

 Acceptability in terms of omitted items. Where measures have recommended prorating for some proportion of missed items the proportions proratable will be reported. If omission rates are high the possible effects of prorating, and the possible biases if omission is associated with any particular demographic or clinical variables, or tends to occur at higher or lower scores across the completed items will be note.

- Floor and/or ceiling effects for items.
- Internal reliability (Cronbach alpha (Cronbach, 1951) and McDonald's Omega (Revelle & Zinbarg, 2008) of scores both for the total participant group completing all items, but also by gender and diagnostic groups and by age for the young participants (as there is evidence (e.g. Twigg et al., 2016) that reliability, as well as score distributions, can vary importantly and statistically significantly with gender and age through adolescence). There has been much argument against the use of Cronbach's alpha, much of it accusing it of doing things Cronbach was careful in 1951 to say it didn't do, fundamentally these criticisms are that it can both underestimate and overestimate classical test theory (CTT) reliability, the latter particularly when a measure is not unidimensional. McDonald's omega corrects the latter issue particularly but alpha has been, and may remain, the dominant statistic reflecting internal reliability hence we will report both.

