- Construct validity in terms of factor analyses within and across measures. We 0 believe that factor analytic methods are often overvalued when applied to short, broad coverage measures of diverse problems, measures designed as much to be good within-individual reflections of change as to be good between-individual comparators. However, both in clinical practice and research all the self-report measures used in the study are used both for comparisons across individuals and to measure change over time hence it is important, as with reporting the internal reliability, to explore factor structure. The within measure exploration will use confirmatory factor analysis (CFA) where either there are widely used scale scores for the measure or where there has been debate in the literature about whether a measure (or scale/score) is unidimesional or has more factors of interpersonal difference. As the indicators (items) are short ordinal scales and as the latent variables are almost certainly not Gaussian in distribution, we will use both maximum likelihood (ML) and diagonally weighted least squares (DWLS) (Li, 2016; Rhemtulla et al., 2012) estimation and appropriate scaled/robust fit

statistics (Satorra & Bentler, 2010) for the estimation method. Assuming the DWLS and robust fit statistics give better fit these will be reported with a note about the ML fit. If numbers allow (n > 250) separate analyses will be conducted by gender, age and diagnosis.

We will explore factorial measurement invariance across first and second completions (exempting items clearly impacted by the restrictions of hospitalisation). We will also explore invariance between groups by gender, sensible age groups (determined partly by cell sizes, here again n > 250) and diagnoses (again, restricted by sufficient cell sizes). For both temporal and between group analyses we expect only quite low levels of invariance as we believe there are very real changes and differences in structure, hence the focus will be more on the magnitude of the impacts on scores of the invariance rather than whether statistically significant invariance is or is not present. If fit to the scale design is particularly bad, exploratory factor analyses will be conducted and reported.

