As well as within-measure analyses, we will also conduct across-measure factor analyses as these allow construct validity to check on where one might expect shared factor structure (i.e. for (Ch)EAT and BITE) or might expect largely unrelated factor structure (i.e. between (YP-)CORE and both (Ch)EAT and BITE). These analyses will be CFA by design structure and EFA if fit to design structure is clearly very poor.

- If some measures/scores show clear fit to unidimensionality, we will conduct Item Response Theory (IRT) analyses to identify cutting points and potential evidence that the conventional scoring of the measures may be suboptimal for cross-sectional comparisons.
- Convergent validity between related measures (EAT-26/CHEAT-26 and BITE) and convergent and divergent validity between them and diagnoses and BMI. These are more conventional explorations than the item level across-measure factor analyses noted above. We will explore scatterplots for marked non-linearity or

clearly non-zero intercepts and, assuming there are not major issues of those kinds, will report Spearman rho and Pearson R correlations with bootstrap confidence intervals. Reporting both correlations maximises comparability with existing literature as Spearman correlations have often been reported in the past, before the widespread availability of bootstrapping, as score distributions are generally not Gaussian. If numbers allow (n > 80) separate analyses will be conducted by gender, age and diagnosis.

Divergent validity/confounding against gender, age, first language, education.
 Distributions will be compared by groups (with sensible age groups) and the simple scattergrams against age inspected. Unless clearly inappropriate Pearson correlations with age, and mean differences by groups, will be reported with bootstrapped CIs.

To explore the psychometrics of change (tranche  $\underline{2}$  and  $\underline{3}$ ):

- Where participants have sufficient completed measures (n > 20) we will to apply P-technique estimation of Cronbach's alpha within individuals, within and across measures. For the small number of participants with the larger number of sufficient completions (n > 40) we will also explore P-technique "factor" structure (actually Principal Component Analyses (PCA)) to show the structures that emerge where the sequences of completed measures within individuals allow this.

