# 4. Evaluation of the care types (inpatient, day hospital, and outpatient).

As with diversity of change, this aim will be explored largely through baseline/termination change broken down by types of care and, if numbers are large enough (to be explored by simulation) also by MLM and survival analysis with type of care as predictor (tranches  $\underline{1}$ ,  $\underline{2}$  and  $\underline{3}$ ).

However, this is clearly not a simple predictor/response relationship and there are two main complicating issues: that participants can have multiple trajectories through types of care, and that the types of care offered will reflect clinical need/severity and, probably to a lesser extent, demographic issues including age, occupation and carer responsibilities.

We expect that only a minority of the participants will receive only a single type of care as almost all who start in inpatient or day hospital care will progress to a less intense type of care and inpatient care unless they are very late recruits (and even then, transitions will be seen in the second, follow-up, phase of data collection). Inpatient care will often be succeeded by day hospital care and that in turn by outpatient care. A further complication is that a subset of participants will have "upward" as well as "downward" transitions and the diversity of trajectories across types of care will only permit robust MLM if only the major and simplest trajectories are analysed treating levels of care as time dependent covariates. For this reason, analyses will be only of the "simple transitions" but presented with clear caveats about the dangers of extrapolating overconfidently to all future clients starting in any of the three care types without taking the real complexities of transitions into account.

The second challenge, that types of care offered will undoubtedly be affected by severity (hence probably strongly correlated with scores on measures) and by some aspects of demography, can only really be explored in terms of associations with scores and with

demographics at baseline by type of care, and for the categories of later care type transitions.

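### The SAP's one interval rule (BCa bootstrap, else percentile) gives a zero-width interval for a simple proportion with no events or all events

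*SAP*

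**What the plan says.** SAP section 1 (Multiple tests and p-value hunting/hacking) sets the scope: "Where possible, 95% confidence intervals (CIs) will be reported for all statistics". It then names the method, "we will report the Bias Corrected Adjusted, (bca) 95% CI from 1000 bootstrap replications", and one fallback, "unless it is not available in which case the percential CI will be used". Proportions are not exempted. The SAP gives no score or exact interval, and it does not mention zero or sparse counts.

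Several planned results are proportions:

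- Primary objective, part (a): "report the RCSC breakdown of change on each measure where it is possible to define the CSC and RCI".
- Secondary objective 2: "the proportions proratable will be reported", along with omission rates.
- Secondary objective 5: initial refusals and withdrawals.

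Secondary objective 4 adds "baseline/termination change broken down by types of care", which makes denominators smaller.

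**The concern.** A bootstrap can only resample what was observed. If nobody in a group falls in a category, no resample contains a case, and the bootstrap carries no information on how large the true rate might be. A rule that must then report the percentile interval reports perfect certainty just where the data are weakest. More replications do not help.

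The SAP makes estimation central. It also declines multiplicity control and relies on reported p values and intervals instead, for an intended readership of clinicians and clinical researchers. Such a reader could take a 95% interval of 0% to 0% at face value.

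**Working it through.** **Inputs.** From the SAP: 95% level, BCa with 1000 replications, percentile fallback. The SAP states no sample size, event count or category rate, so there is no figure of its own to reproduce beyond the nominal 95%. The sizes (n = 30 to 1000) and true rates (p = 1% to 10%) are assumptions. Two sizes echo thresholds that the SAP sets for other purposes: "If numbers allow (n > 80) separate analyses will be conducted by gender, age and diagnosis" for correlations and "If numbers allow (n > 250) separate analyses will be conducted by gender, age and diagnosis" for factor analyses.

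**Step 1: zero events.** With x = 0 every resampled proportion is 0. The BCa acceleration becomes 0/0; a standard routine returned no BCa interval for 0/80 and a percentile interval of exactly 0 to 0. By symmetry, x = n gives 100% to 100%.

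The alternatives at x = 0 are:

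- Wilson upper limit = z²/(n + z²), with z² = 3.84. For n=30: 3.84/33.84 = 11.4%. For n=80: 3.84/83.84 = 4.6%.
- Clopper-Pearson upper limit = 1 - 0.025^(1/n). This gives 11.6% at n=30 and 4.5% at n=80.

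**Step 2: cap on coverage.** A zero count always misses a true rate above zero, so coverage cannot exceed 1 - P(X=0) = 1-(1-p)^n. At n=80, p=2%: 1 - 0.98^80 = 1 - 0.199 = 80.1%.

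**Step 3: exact coverage.** The binomial probabilities of all counts whose interval contains p were summed. Percentile limits are quantiles of Binomial(n, x/n)/n. BCa used a bias correction from P(X* < x) and the empirical acceleration, with the fallback at x = 0.

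| n | p | expected events | cap | SAP rule | Wilson |
|---|---|---|---|---|---|
| 30 | 1% | 0.3 | 26.0% | 26.0% | 96.4% |
| 80 | 1% | 0.8 | 55.2% | 54.4% | 95.3% |
| 30 | 5% | 1.5 | 78.5% | 78.2% | 93.9% |
| 50 | 3% | 1.5 | 78.2% | 77.8% | 93.7% |
| 80 | 2% | 1.6 | 80.1% | 79.6% | 97.8% |
| 100 | 2% | 2.0 | 86.7% | 86.6% | 94.9% |
| 80 | 3% | 2.4 | 91.3% | 91.0% | 96.7% |
| 250 | 1% | 2.5 | 91.9% | 91.5% | 95.9% |
| 100 | 3% | 3.0 | 95.2% | 94.9% | 96.9% |
| 80 | 5% | 4.0 | 98.3% | 91.2% | 93.7% |
| 250 | 2% | 5.0 | 99.4% | 95.6% | 96.3% |
| 500 | 1% | 5.0 | 99.3% | 95.5% | 96.2% |

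Simulation with 1000 replications and 4000 data sets per setting agrees: at n=80, BCa coverage was 54%, 79%, 91% and 96% for p = 1%, 2%, 5% and 10%.

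**Step 4: where the loss comes from.** In every row up to 2.5 expected events, coverage is within 1 point of the cap, so nearly all the loss is the zero count. The n=80, p=5% row differs. There a count of one also misses, because its upper limit is 3/80 = 3.75%. The probability of that count is 80 × 0.05 × 0.95^79 = 7.0%, which takes the cap of 98.3% down to about 91%. Wilson covers only 93.7% in that setting.

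**The case against.** **The SAP qualifies the rule.** It promises intervals only where possible, and some software refuses to give one for constant data. On that reading the table would show a missing interval, not 0% to 0%. This is fair, but it leaves the sparsest categories with no interval and names no alternative.

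**The main results are untouched.** Mean change, effect sizes and correlations do not depend on this. The SAP calls its methods exploratory and descriptive, no decision rule uses these intervals, and an observed 0/n stays visible. All of this stands and limits the severity.

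**The subgroup setting is partly assumed.** The SAP plans RCSC on each measure, and explores predictors through models of termination scores, not through RCSC in each subgroup. Care type is the clearest breakdown that could carry RCSC. The thresholds of 80 and 250 belong to other analyses. This also stands.

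**Stronger readings that the SAP does not support:**

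- A reader might infer that the rule would hide harm by declaring deterioration impossible. The SAP names neither deterioration nor any harm signal. A deterioration category is only a likely part of an RCSC breakdown.
- A reader might infer that intervals for rare proportions are too short in general, including at one or two events. The low coverage at few expected events is almost wholly the zero-count failure. Results at a count of one depend on how BCa treats ties: for 1/80 the upper limit is 3.75% with a strict count and 6.8% with one that splits ties, against 6.7% for Wilson.
- A reader might infer that every proportion needs a Wilson interval. Termination categories are right-censored and analysed by survival methods, and repeated measures within a participant are not independent. A plain binomial interval would be wrong for both.

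**Conclusion.** The defect is real but narrow. As written, the rule gives a zero-width interval, or at best none, for any simple proportion with 0 or n events, whatever n is. Coverage is then bounded by 1-(1-p)^n. Over the assumed settings it runs from 26% to 87% at up to 2 expected events, is about 91% near 2.5, and is roughly 91% to 97% from about 3.

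The zero-count result needs no assumption beyond the SAP's own wording. The coverage figures rest on assumed sizes and rates and on independent participants. Whether RCSC, omission or refusal cells fall in the bad range cannot be shown from the SAP. Severity is minor to moderate.

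**What to change.** Add to SAP section 1:

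*For simple proportions of independent participants (e.g. RCSC categories, refusal and omission rates) the 95% CI is the Wilson interval, or Clopper-Pearson when the count is 0 or n. Censored termination outcomes use the interval from the survival analysis. Proportions with repeated observations per participant use a method that allows for clustering. BCa is kept for other statistics.*

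The cost is this short addition and wider intervals for rare categories. No other analysis changes. Over the settings examined, Wilson covered 91% to 98% and Clopper-Pearson 95.5% to 99.7%.

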#### 2. Planned and emergent analyses

Many analyses will be conducted to address the study objectives and these are summarised below. As noted, the complexity of the data will certainly lead to the performance of emergent analyses. These will always be defined as such, against this DAP, in any presentations, reports or papers. All publications will be made with the (Altman & Moher, 2013) transparency statement which will apply to the distinction between *a priori* and emergent analyses as much as to all important issues to be acknowledged transparently.

The analysis timing has been designed in three tranches.

- The first tranche will focus on the baseline data for participants recruited during the first three years. The most important focus will be to establish the baseline distributions of variables that will be used later to measure change, the psychometric properties of

those measures, the differences between clinical centers, and any strong associations between baseline variables likely to raise issues about confounding in the subsequent analyses of change.

- The second tranche will contain all data collected by the end of October 2020: the endof the intensive data collection phase. When analysing these data, the focus will be on change: changes in sociodemographic variables (assessed annually) and clinical interventions but primarily changes in the key clinical outcome variables of the questionaire scores and BMI.
- The third tranche will add the follow-up information for all the participants recruited to October 2020 as and followed-up, where in continued clinical contact with the services, to November 2025. The main analyses for this tranche will largely follow the explorations of change, its diversity and its predictors as from the second tranche.

Here we present the a priori analyses planned for each objective and broken down by tranche.

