(c) Survival analysis (e.g. Allgulander & Fisher, 1986; Singer & Willett, 2003; Willett & Singer, 1993)for time to terminations by category of termination. These analyses focus on the time spans between entry into treatment and termination which are not so focal in (a) and (b). The particular strength of survival analysis for a naturalistic cohort follow-up study is that it address the inevitable right censoring of follow-up. That is that at termination of intensive data collection some participants will be still in treatment so their "outcome" is only know to this point and how long each has been in treatment to that point will be very varied with some of the very first participants joining the study potentially still in treatment near three years on though many of those early participants will have terminated treatment so not be "right censored". Of course far more of the recently recruited participants will be still in treatment and their change only known to that point.

The uncertainties arising from this censoring of outcomes is considered in, and visible in, the findings of survival analyses. We will analyse time to completion of therapy by category of termination and also analyse how baseline predictor variables impact on the slope of those curves. Different survival analytic methods make different assumptions about the relationships between predictors and the time curves, notably whether there is "parallelism" of curves across groups, or not, and these issues will be explored, and the appropriate analyses reported.

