# Secondary objectives:

### 1. Describe the study participants.

To establish the baseline distributions of variables (i.e., BMI, CORE, EAT-26/ChEAT-26, and BITE) that will be used later to measure change (tranche 1). The aims are:

- To describe the distributions of scores at baseline on the change measures and how these relate to other variables:
  - demographic variables, primarily age and gender;
  - o clinical variables primarily diagnosis, care type and medication and,
  - both because of the interest in this within ITA, and for the MLM analyses
    of change (above) and the differences between clinical centres.

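### The SAP does not say that BMI change in young participants is standardised for age and sex, or analysed apart from adults, so the change estimates could include normal growth

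*SAP*

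**What the plan says.** SAP section 2 (Planned and emergent analyses) describes the second tranche as concerned with "primarily changes in the key clinical outcome variables of the questionaire scores and BMI". Secondary objective 1 again lists BMI among the baseline variables: "i.e., BMI, CORE, EAT-26/ChEAT-26, and BITE) that will be used later to measure change". No section mentions a BMI z-score, centile, percentage of median or other growth reference.

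Young people are in the cohort. Secondary objective 2 plans reliability estimates "also by gender and diagnostic groups and by age for the young participants" and plans factor analyses "between (YP-)CORE and both (Ch)EAT and BITE", so youth versions of the questionnaires are in use.

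Under the primary objective, analysis (a) reports mean change with d2 (divided by the baseline SD) and dz (divided by the SD of change). Analysis (b) fits multilevel slopes on time. Age is among the baseline predictors in both. The General statistical approach states that there is no randomisation or experimental control.

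On duration, analysis (c) foresees "some of the very first participants joining the study potentially still in treatment near three years on". Section 2 says of the data cut: "The second tranche will contain all data collected by the end of October 2020". The third tranche continues to November 2025 for participants still in clinical contact.

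**The concern.** In a growing person BMI rises with age even when position relative to peers does not move. Without a comparison group this rise does not cancel; it goes straight into the change estimate. Where weight gain is the hoped-for direction, part of a reported gain could be growth, and a young person falling behind peers could still show a positive change. This happens within any single diagnosis, so splitting by diagnosis does not deal with it.

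The SAP is alert to age elsewhere: it notes that questionnaire reliability and score distributions vary through adolescence. It has no counterpart for BMI. Analysis (b) names two complications for the trajectories, the staggered start of centres and the pandemic, and growth is not one of them.

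The scale should be settled now, because section 2 says that emergent analyses are identified against this document. An age-standardised BMI brought in later would have to be labelled emergent, or the choice of scale would stay open after the data had been seen.

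**Working it through.** **No figure to reproduce.** The SAP gives no BMI mean, SD, expected change, age mix or typical duration. Every growth, SD and age input below is an assumption.

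**Step 1: follow-up spans.** The phrase about nearly three years, set against the end of October 2020, implies a start near November 2017 (inferred). From then to the end of October 2020 is 3.0 years, and to the end of November 2025 is 8.1 years. Both are maxima.

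**Step 2: size of growth on the kg/m² scale.**

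- Mean drift = growth per year × growing years × share growing.
- d2 from growth alone = mean drift / baseline SD.
- Assumed inputs: growth 0.2 to 0.8 kg/m² per year; baseline SD 3 to 5 kg/m²; share growing 100% (growing participants only) or 25% (whole cohort).

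| Group | Growing years | Mean drift, kg/m² | d2 |
|---|---|---|---|
| Growing participants | 1 | 0.2 to 0.8 | 0.2/5 = 0.04 to 0.8/3 = 0.27 |
| Whole cohort, 25% growing | 1 | 0.05 to 0.20 | 0.05/5 = 0.01 to 0.20/3 = 0.07 |
| Growing participants | 3 | 0.6 to 2.4 | 0.6/5 = 0.12 to 2.4/3 = 0.80 |
| Whole cohort, 25% growing | 3 | 0.15 to 0.60 | 0.15/5 = 0.03 to 0.60/3 = 0.20 |

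The three-year rows apply only to participants who grow throughout all three years, so they are upper limits for that span.

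**Step 3: does entering baseline age remove growth?** In a least-squares regression of termination BMI on baseline BMI and age, the fitted value at the means of the predictors equals the mean termination value. The age-adjusted mean change at average age therefore equals the unadjusted mean change. A simulation with zero treatment effect shows the same. Its assumptions are ages uniform from 11 to 40 (24% under 18), growth ending at 18, baseline SD 3, residual SD 1.5, and follow-up uniform from zero to the stated maximum. Each cell gives results for growth of 0.2 / 0.5 / 0.8 kg/m² per year.

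| Follow-up up to | Mean change, under 18 | d2, under 18 | Mean change, all | Age-adjusted mean change, all |
|---|---|---|---|---|
| 1 year | 0.097 / 0.240 / 0.384 | 0.032 / 0.080 / 0.128 | 0.024 / 0.059 / 0.088 | 0.024 / 0.059 / 0.088 |
| 3 years | 0.268 / 0.649 / 1.026 | 0.090 / 0.216 / 0.342 | 0.071 / 0.159 / 0.248 | 0.071 / 0.159 / 0.248 |
| 8 years | 0.495 / 1.236 / 1.985 | 0.166 / 0.411 / 0.664 | 0.125 / 0.299 / 0.481 | 0.125 / 0.299 / 0.481 |

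The last two columns agree: adjustment leaves the drift where it was. In the multilevel model, similarly, age as a predictor of slope shows that slopes differ, but the overall slope still contains growth.

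**Step 4: does drift keep pace with time?** No. At 0.5 kg/m² per year, going from a maximum of 3 to 8 years multiplies the time by 8/3 = 2.67, but the under-18 change by only 1.236/0.649 = 1.90, because growth ends.

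**Step 5: the alternative scale.** A participant who grows normally and holds the same position relative to the reference has an expected change of zero on an age- and sex-standardised scale.

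**The case against.** The strongest reply is that the SAP is silent on the scale of BMI and does not make a wrong choice. It says only BMI, calls itself a shortened version of a much larger document, and is meant to complement a protocol paper that is not at hand; the derivation of BMI in minors may be given there. That stands against a reader who would infer that the SAP has chosen raw BMI and that growth will be counted as treatment effect. The text supports only that it could be. It does not remove the point: the scale on which change is analysed belongs in an analysis plan, and taken as written BMI means BMI in kg/m².

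Age is also handled in part. Tranche 1 relates baseline values to age and looks for confounding, age is a predictor in (a) and (b), and subgroups will be explored. This can expose age-dependent change, but Step 3 shows that it does not correct the overall estimate.

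Some wording under (a) may not cover BMI at all. "As well as reporting the global aggregate mean shifts with bootstrap 95% CI for each score" speaks of scores, whereas section 2 names questionnaire scores and BMI separately. The Jacobson plots also refer to scores, and the reliable and clinically significant change breakdown is limited to measures where its criteria can be defined. Contamination of individual-level BMI classifications is therefore not shown. That BMI enters the mean change and the multilevel models is an inference, though a strong one for a key change outcome.

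Finally, a reader might take about eight years as the period over which growth accumulates. It is a maximum for those still in contact, analysis (a) ends at termination, and growth stops.

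**Conclusion.** The point holds as a gap in specification with a foreseeable direction of bias. BMI is a key change outcome, adolescents are included, there is no control group, and neither age- and sex-standardisation nor a separate BMI analysis of the young is stated. Followed as written, the plan lets normal growth into the effectiveness estimate for young participants.

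The size cannot be fixed from the SAP. Under the assumptions of Step 2, growth alone is material for the growing participants and probably small over one year for the cohort as a whole. The whole-cohort figure depends directly on the share still growing, which is not given.

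Two stronger readings are not supported. One is that most or all of any BMI gain would be growth: the SAP gives no expected gain to compare with. The other is a very large spurious dz at three years. An assumed SD of change of 2 kg/m² would give 2.4/2 = 1.2, but an SD of 4 gives 2.4/4 = 0.6, and both require uninterrupted growth at the highest assumed rate. The SAP supplies no SD of change, so dz is left unquantified here.

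The correction should be made before change is analysed, with moderate confidence in its practical importance.

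**What to change.** Add to analyses (a) and (b), for all tranches in which change is analysed:

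- Name one growth reference. Define the young stratum as participants below a stated baseline age, equal to the upper age limit of that reference.
- In that stratum, analyse BMI as a percentage of the age- and sex-specific median at the date of each measurement. Once a participant passes the upper age limit, hold the reference at that limit so that each trajectory stays on one scale.
- Keep BMI in kg/m² for adults.
- Report mean change, d2, dz and multilevel slopes separately in the two strata, and do not pool raw BMI change across them.
- Show raw BMI in the young as descriptive only.

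If the protocol paper or the longer analysis document already defines such a scale, a cross-reference and the stratification rule would be enough.

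The cost is some SAP text and a look-up from age, gender and BMI, which the SAP already analyses. The downside is two BMI results instead of one pooled figure, with less precision in each.
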